PROTOCOL TITLE: Virtual Pediatric Trauma Center

ClinicalTrials.gov – Study Protocol and Statistical Analysis Plan

Title: Improving Family-Centered Pediatric Trauma Care: The Standard of Care Versus the Virtual Pediatric Trauma Center

NCT Number: NCT04469036

Document Date: 09/22/2022

Protocol Title

Title: *Virtual Pediatric Trauma Center*

Protocol Version Date: 2022-09-22

1) Objectives

[figure not shown]
- **Aim #1a:** To compare the parent/family experience of care and distress at 3-days and 30-days following a childhood injury requiring an emergency department visit in a non-pediatric trauma center under the current standard model of care and the VPTC model of care.
 - Null Hypothesis: Measures of parent/family experience of care and measures of distress will be similar between the two models of care.
- **Aim #1b:** To compare the frequency of potentially avoidable transfers (PAT) and transfers in a non-pediatric trauma center under the current standard model of care and the VPTC model of care.
 - Null hypothesis: Frequency of PATs and transfers will be similar between the two models of care.
- **Aim #2:** To compare 30-day healthcare utilization between injured children cared for under the current standard model of care and the VPTC model of care.
 - Null Hypothesis: Hospitalizations, re-hospitalizations, primary and specialty care visits will be similar between the two models of care.
- **Aim #3:** To compare the out-of-pocket costs and financial burdens experienced by parents/families at 3-days and 30-days following a childhood injury requiring an emergency department visit in a non-pediatric trauma center under the current standard model of care and the VPTC model of care.
 - Null Hypothesis: Out-of-pocket costs and financial burdens for parent/families will be similar between the two models of care.

2) Background

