In summary, rationale for the waiver of HIPAA and waiver of consent for the data abstraction include: (1) The use or disclosure of protected health care information involves no more than minimal risk; (2) the research could not practicably be conducted without the waiver or alteration; and (3) the research could not practicably be conducted without access to and use of the PHI.

All study personnel involved in this proposed project have received Human Subjects Protection and HIPAA education.

Data Analysis Plan/Statistical Procedures:

Regression analyses will be conducted within a generalized linear mixed model framework for multilevel data (patients nested within hospitals), with random effects for hospitals specified to account for unmeasured sources of between-unit heterogeneity.⁶⁵⁻⁶⁷ A within-site time-varying binary indicator (VPTC vs. standard of care) will be included in the model to permit estimating the key contrasts of interest. For linear-normal mixed models (e.g., experience of care and distress), effect sizes will be adjusted mean differences; for binary and count outcomes fitted with logistic and Poisson regression models, respectively, effect sizes will be adjusted odds and rate ratios, respectively. For outcomes assessed at both 3-days and 30-days after injury, we anticipate estimating time point-specific contrasts of the VPTC vs. standard of care groups. To do this, models will also include a binary indicator for time point (3 day vs. 30 day) as well as interactions of time point with the time-varying treatment group indicator. Additional independent variables will include a parsimonious and pre-specified set of patient-level effects to account for study design effects and to improve the precision of estimated effects, accounting for known sources of heterogeneity.^{66,68,69} To account for confounding by calendar time in our stepped-wedge design,⁶² we will compute each patient's date at enrollment in the study and use fractional polynomial modeling to determine the order of polynomial (linear, quadratic, cubic, etc.) to specify the calendar date of enrollment effects, to account for temporal effects.⁷⁰ A senior health economist will conduct the economic analyses relevant to the financial burdens experienced by parent/family members. Additional details for each aim and outcome are provided below.

8) Data and/or Specimen Banking

N/A

9) Provisions to Monitor the Data to Ensure the Safety of Subjects

N/A

10) Withdrawal of Subjects

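### The Poisson model for count outcomes makes no allowance for overdispersion between children in the same hospital, so Aim 2 intervals for 30-day visits may be too narrow

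*Combined protocol and SAP*

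**What the plan says.** Section 7, under Data Analysis Plan/Statistical Procedures, puts all regressions in a mixed-model framework with patients nested in hospitals, "with random effects for hospitals specified to account for unmeasured sources of between-unit heterogeneity". No other random effect is named. The model follows the outcome type: "for binary and count outcomes fitted with logistic and Poisson regression models", with results given as adjusted odds ratios and adjusted rate ratios in that order.

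Two further components enter the models. One is a set of covariates: "Additional independent variables will include a parsimonious and pre-specified set of patient-level effects". The set is not listed. The other is calendar time, for which the analysts will "use fractional polynomial modeling to determine the order of polynomial (linear, quadratic, cubic, etc.) to specify the calendar date of enrollment effects".

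Aim 2 in Section 1 is "To compare 30-day healthcare utilization between injured children cared for under the current standard model of care and the VPTC model of care", with the null hypothesis "Hospitalizations, re-hospitalizations, primary and specialty care visits will be similar between the two models of care". Neither section labels these outcomes as counts or as yes/no. The analysis section closes with "Additional details for each aim and outcome are provided below", but in the text available Section 8 follows directly and no such details appear.

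**The concern.** A Poisson mixed model fixes the variance at the mean once the fixed and random effects are given. A hospital effect takes up differences between hospitals. It cannot take up differences between two children at the same hospital.

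The population is broad: any injured child under 18 discussed in a transfer call to trauma surgery, orthopedic surgery or neurosurgery. The need for follow-up visits plausibly differs widely among such children. Whatever part of that variation the covariates do not explain stays in the data as overdispersion, and the stated model has nowhere to put it.

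The rate ratio is not the main casualty; its standard error is. Intervals that are too narrow could support a claim that the two models of care differ in visits, in either direction, when they do not. Section 14 itself says that utilization might get worse as well as better, so an error either way matters.

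**Working it through.** **No figure to reproduce.** The documents state no sample size, alpha, mean count or dispersion for Aim 2. What follows is the size of the effect under stated assumptions.

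**Inputs from the documents**
- Poisson for counts, hospital random effects, covariates and a calendar-time polynomial (Section 7).
- A 30-day window, the same for every child (Section 1, Aim 2), so unequal follow-up is not a planned source of extra variation.
- 10 hospitals in the design table and 13 eight-week periods, with one hospital crossing over at a time (Section 6).

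**Assumed inputs:** the conditional ratio φ, mean counts, the negative binomial parameter k, 5 children per hospital-period, and a between-hospital SD of 0.3 on the log scale.

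**Step 1: analytic size.** Let φ be the ratio of variance to mean given hospital, covariates and calendar time. The Poisson standard error is too small by a factor √φ, so a two-sided test at nominal 5% has true size 2 × (1 − Φ(1.96/√φ)).

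| φ (assumed) | √φ | 1.96/√φ | True size | Coverage of 95% interval |
|---|---|---|---|---|
| 1.0 | 1.000 | 1.960 | 5.0% | 95% |
| 1.1 | 1.049 | 1.869 | 6.2% | 94% |
| 1.5 | 1.225 | 1.600 | 11.0% | 89% |
| 2 | 1.414 | 1.386 | 16.6% | 83% |
| 3 | 1.732 | 1.132 | 25.8% | 74% |

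**Step 2: link to the mean count.** For negative binomial counts φ = 1 + mean × k. With k = 1:
- mean 0.05: φ = 1.05, size 5.6%
- mean 0.1: φ = 1.1, size 6.2%
- mean 0.5: φ = 1.5, size 11.0%
- mean 1: φ = 2, size 16.6%
- mean 2: φ = 3, size 25.8%

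At mean 0.5, taking k = 0.5 or k = 2 instead gives 8.0% or 16.6%. The harm is therefore slight for rare events and becomes material at roughly 0.5 visits per child or more.

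**Step 3: simulation in the stepped-wedge layout.** Null data were generated for 10 × 13 × 5 = 650 children, 1,000 runs per row, with quadratic time. Hospital was fitted as a fixed effect in place of the random intercept. Rejection rates at nominal 5%:

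| Mean, k | φ | Poisson | Poisson with estimated scale | Robust variance |
|---|---|---|---|---|
| 1, 0 | 1.0 | 5.1% | 5.0% | 4.7% |
| 0.1, 1 | 1.1 | 5.7% | 5.0% | 5.1% |
| 0.5, 1 | 1.5 | 11.3% | 6.1% | 6.1% |
| 1, 1 | 2 | 18.9% | 5.9% | 5.8% |
| 2, 1 | 3 | 26.5% | 5.6% | 5.5% |
| 1, 2 | 3 | 25.1% | 5.8% | 5.2% |

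The simulation error near 5% is √(0.05 × 0.95/1000) = 0.7 percentage points. The simulation agrees closely with Step 1, and an estimated scale brings the size back to 5.0–6.1%. The negative binomial fit itself was not simulated, and no patient covariates were included.

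**Step 4: what covariates can do.** Suppose 10% of children average 6 visits and 90% average 1, with Poisson variation within each group. The mean is 0.1 × 6 + 0.9 × 1 = 1.5. The between-group variance is 0.1 × 0.9 × 5² = 2.25. The marginal ratio is 1 + 2.25/1.5 = 2.5. If a covariate identifies the two groups, the conditional ratio is 1 and there is no inflation. If covariates remove half the excess, the ratio is 1.75 and the size is about 14%.

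**The case against.** The strongest reply is that the plan does adjust for patient characteristics. Section 6 lists Glasgow Coma Score, diagnosis codes, critical care use and age among the abstracted variables. If the covariates capture most of the difference in severity, the conditional ratio may be close to 1. This stands as a limit on size: the ratio that matters is conditional, and Step 4 shows how far adjustment can go. It does not remove the point, because the covariate set is described as small and is not listed, and the model has no safeguard for what the set misses.

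A second reply is that the plan promises outcome-level details, so silence on dispersion does not show that a bare Poisson model is locked in. That also stands, but Poisson is the only count model in the available text.

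A reader might go further and infer that standard errors for hospitalization and re-hospitalization will be too large, since such outcomes are nearly yes/no and vary less than Poisson. The documents do not support this. They never assign those outcomes to Poisson, and the logistic model in the same sentence already allows a yes/no analysis. Any figure would also depend wholly on the assumed rate. At 60% the ratio is 1 − 0.6 = 0.4 and the size about 0.2%; at 5% the ratio is 0.95 and the size about 4.4%.

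**Conclusion.** The point holds for visit counts and is conditional. The plan names Poisson with hospital random effects and provides nothing for extra variation between children in the same hospital. If visits remain overdispersed given hospital, covariates and calendar time, the true size of a nominal 5% test is about 11% at a ratio of 1.5 and 17% at a ratio of 2. For rare counts it is about 6% (mean 0.1, k = 1).

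This rests on reading visits as counts, which the plan does not state, and on assumed means and dispersions. A reader might infer that the Aim 2 intervals are bound to be wrong unless the overall variance equals the mean. That is too strong: the condition concerns the conditional variance, and the documents contain no data that show overdispersion. The change is worth making because it is cheap and because settling the count model after seeing the data would leave room for choice. It affects inference on one part of Aim 2, not the trial as a whole.

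**What to change.** For 30-day primary and specialty care visits, replace Poisson with a negative binomial mixed model, or with Poisson and an estimated scale. Name one of the two in advance. Keep the hospital random effect, the patient covariates, the calendar-time terms and the rate ratio. In the same place, state for each Aim 2 outcome whether it is a count or yes/no; hospitalization and re-hospitalization can be yes/no under the logistic model already in the plan.

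If a robust variance clustered by hospital is preferred, it needs a small-sample correction with about ten hospitals. The robust variance in the simulation was not clustered by hospital.

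The cost is a sentence or two in the analysis plan, and intervals wider by a factor of √φ when counts are overdispersed (1.22 at a ratio of 1.5, 1.41 at 2). If Poisson holds, little is lost: at φ = 1 the scaled test rejected in 5.0% of runs against 5.1% for plain Poisson.

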Parents/guardians of eligible patients will be contacted within 3-days of the eligible emergency department visit to complete the first survey. They will then be asked to complete surveys at 30-, 60-, and 90-days after the eligible emergency department visit. They will be given until 104 days after the eligible emergency department visit to complete the final survey.

The study team will complete primary analyses by May 31st, 2023.

5) Study Endpoints

Transfer consultation data will be collected until March 31st, 2024.

Surveys will be collected until March 14th, 2023.

6) Procedures Involved

Systems Level Intervention

To compare our parent, family, community and provider informed outcomes between the current standard of care and the VPTC, we will use a prospective stepped-wedge trial design,⁶² which has important advantages over alternative designs. First, with the stepped-wedge design, changes in the quality and standards of pediatric trauma care over time can be accounted for, unlike a simple pre-test, post-test study design where

PROTOCOL TITLE: Virtual Pediatric Trauma Center

changes in care could be confounded by temporal changes and secular trends. Second, in common with a cluster randomized design, and in contrast to patient-randomized designs, our design minimizes contamination bias that could arise among researchers and participants when patients at the same site have been concurrently randomized to two different models of care. In addition, the stepped-wedge design has an important statistical power advantage over a parallel-groups cluster-randomized trial. The latter design suffers a loss of statistical power that arises from within-cluster correlation (ICC), even when ICC is as modest as 5%, a typical value for process-of-care outcomes.⁶³ The presence of positive intra-cluster correlation has the opposite effect in a stepped-wedge design, because in that design, the contrast of interest is a “within-cluster” contrast, so that the cluster serves as its own control, increasing the effective sample size and resulting statistical power.⁶⁴

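### Section 7 pools each parent's 3-day and 30-day surveys in one model with hospital random effects only, so the time-specific VPTC standard errors are modestly too small

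*Combined protocol and SAP*

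**What the plan says.** Under Data Analysis Plan/Statistical Procedures in Section 7, the framework is for "multilevel data (patients nested within hospitals), with random effects for hospitals specified to account for unmeasured sources of between-unit heterogeneity". That is the only hierarchy and the only random component named. For outcomes assessed at both 3 and 30 days the plan expects contrasts specific to each time point, and "models will also include a binary indicator for time point (3 day vs. 30 day"), together with time-point-by-treatment interactions. Patient-level effects appear in the list of further independent variables, so they are covariates. Calendar date of enrolment enters as a polynomial, with no stated interaction with time point.

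Section 4 (Study Timelines) shows that the surveys are repeated on the same people. Of the parents contacted for the first, 3-day survey it says: "They will then be asked to complete surveys at 30-, 60-, and 90-days after the eligible emergency department visit". Section 6 repeats the schedule.

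The aims that use both time points are Aim 1a, "To compare the parent/family experience of care and distress at 3-days and 30-days following a childhood injury", and Aim 3, "To compare the out-of-pocket costs and financial burdens experienced by parents/families at 3-days and 30-days following a childhood injury".

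The statistical text closes with "Additional details for each aim and outcome are provided below", but Section 8 follows and no such details appear. No residual covariance, GEE or robust variance is named anywhere.

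**The concern.** Two reports by one parent about one child's injury, 27 days apart, are very unlikely to be independent given the hospital. A model with a hospital effect alone counts them as two separate pieces of information.

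It might seem that contrasts specific to a time point are immune, since each parent contributes only one survey to each. They are not, because the hospital effects and the calendar trend are shared across the two time points. Each contrast therefore borrows from the other survey as if it came from a different parent.

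What is at stake is the precision claimed for experience of care and distress under Aim 1a: intervals too narrow and a false-positive rate above 5%. The same holds for Aim 3 if this model is used there. That is an inference, because Section 7 leaves the economic analyses to a health economist. Outcomes recorded once per patient, such as transfers and potentially avoidable transfers (Aim 1b), are unaffected.

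**Working it through.** The plan states no sample size, standard deviation or within-parent correlation, so it has no figure to reproduce.

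**Inputs from the protocol**
- 10 hospitals, 13 eight-week periods, one hospital switching per period (Section 6, design table).
- Hospital random intercept, polynomial calendar time, time point, and treatment by time point (Section 7).
- ICC 0.05: Section 6 gives 5% as typical for process-of-care outcomes. Its use for survey scores is an assumption.

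**Assumed**
- 5 parents per hospital-period; total variance 1.
- Within-parent residual correlation r = 0.3, 0.5, 0.7.
- Cubic calendar time (linear or quadratic changes the ratios by 0.002 or less).
- Normal outcomes. Binary and count outcomes were not computed.

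**Formulas**
- V0 = covariance with the hospital effect only (the planned model). V1 = V0 plus r times the residual variance between a parent's two surveys.
- Model variance: (X'V0⁻¹X)⁻¹.
- True variance of the same estimate: (X'V0⁻¹X)⁻¹ (X'V0⁻¹V1V0⁻¹X) (X'V0⁻¹X)⁻¹.
- Implied type I error: 2[1 − Φ(1.96 × model SE / true SE)].

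**Why the errors do not cancel.** With complete surveys a time-specific contrast is the average of the two contrasts plus or minus half their difference, so its variance is Var(average) + Var(difference)/4. In the planned model these parts make up 0.743 and 0.257 of the total. The average is the larger part because it must be separated from the hospital effects and the calendar trend, whereas those cancel from the difference. Ignoring r understates the first part and overstates the second. At r = 0.5, model SE / true SE is 0.825 for the average and 1/√(1 − 0.5) = 1.414 for the difference. Hence

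true / model variance = 0.743/0.825² + 0.257/1.414² = 1.092 + 0.129 = 1.22,

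and model SE / true SE = 1/√1.22 = 0.905 (0.906 without rounding). The implied type I error is 2[1 − Φ(1.96 × 0.906)] = 7.6%.

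**Results** at r = 0.3 / 0.5 / 0.7. Simulations used REML with 3,000 runs per setting and z-tests at 5%.

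| Setting | Model SE / true SE | Implied type I error, % | Simulated, hospital effect only, % | Simulated, parent intercept added, % |
|---|---|---|---|---|
| (1) Complete, 3-day | 0.940 / 0.906 / 0.875 | 6.5 / 7.6 / 8.6 | 6.3 / 8.6 / 9.1 | 5.4 / 5.8 / 5.6 |
| (1) Complete, 30-day | same | same | 7.2 / 8.3 / 9.0 | 5.5 / 6.0 / 5.7 |
| (2) 60% return at 30 days, 3-day | 0.951 / 0.921 / 0.895 | 6.2 / 7.1 / 7.9 | 5.8 / 7.4 / 9.3 | 5.2 / 5.9 / 5.9 |
| (2) 60% return at 30 days, 30-day | 0.962 / 0.938 / 0.917 | 5.9 / 6.6 / 7.2 | 5.6 / 6.3 / 8.9 | 5.0 / 5.0 / 6.2 |
| (3) Calendar trend by time point, complete | 0.976 / 0.962 / 0.948 | 5.6 / 5.9 / 6.3 | not run | not run |
| (4) Calendar trend and hospital effects both by time point, complete | 1.000 at each r | 5.0 | not run | not run |

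At r = 0 the planned model rejects 5.5% and 5.4% of the time (complete) and 5.0% and 4.8% (60% return).

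In setting (1), varying the ICC over 0.01-0.10 or the cell size over 2-10 parents gives a shortfall of 5-13%. Pairing the extremes of both gives about 4-14%.

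The interaction standard error errs the other way. It is too large by 20 / 41 / 83% with complete surveys and 14 / 26 / 45% with 60% return. No stated aim tests that difference.

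**The case against.** The strongest reply is that this reads silence as a defect. Section 7 describes a framework, says the time-specific contrasts are anticipated, does not assert independence, and points to further details that may exist in a fuller text. That limits what can be said about the team's intent. It does not change what an analyst would fit from the posted plan, which specifies its random effects and names hospitals only. If a parent-level term is already intended, writing it down costs a sentence.

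Second, the shortfall depends on modelling choices. It is zero at r = 0, and it vanishes if both the calendar trend and the hospital effects are allowed to differ by time point (setting 4). This is correct, but Section 7 states neither interaction, and shared effects are the plainer reading.

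Third, not all of the simulated excess comes from the omission. The tests are z-tests with 10 hospitals, the Monte Carlo error is about 0.4 percentage points at a 5% rate (√(0.05 × 0.95/3000) = 0.004), and rates after the fix still reach 6.2%. This stands. The fair comparison is planned against corrected: at 60% return and r = 0.3 it is only 5.8 against 5.2% and 5.6 against 5.0%, while with complete surveys and r = 0.7 it is 9.1 against 5.6% and 9.0 against 5.7%.

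Finally, the effect is small when 30-day return is low, and point estimates are not shown to be biased. Both are true, and they are why the shortfall is called modest.

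**Conclusion.** The concern holds. As written, the model for outcomes measured at 3 and 30 days omits the correlation between a parent's two surveys, and its time-specific VPTC standard errors are too small whenever that correlation is positive and the hospital and calendar effects are shared across time points. For r of 0.3 to 0.7 the shortfall is about 6-13% with complete surveys, 4-10% with 60% return at 30 days, and 2-5% if the calendar trend differs by time point. The omission and the direction of the error are clear from the text. The size rests on assumed values of r, cell size, ICC and return, and on normal outcomes. This should be fixed before analysis, but it does not threaten the design.

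**What to change.** In Section 7, for every outcome measured at both 3 and 30 days, add a parent/patient random intercept nested in hospital, or an unstructured 2x2 within-patient residual covariance, and take the 3-day and 30-day VPTC contrasts from that model. State whether the same model applies to the Aim 3 outcomes.

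Fitting each time point separately is also valid but less precise. In setting (1) its standard error is 0.1278, against 0.1145 / 0.1186 / 0.1225 for the correct joint model at r = 0.3 / 0.5 / 0.7. The ratios are 1.116 / 1.078 / 1.043, or about 4-12% larger.

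The cost is one sentence of plan wording and one extra variance term, with no new data. Compared with the planned model, the time-specific intervals widen by about 6 / 10 / 13% with complete surveys. With 60% return they widen by 5 / 7 / 9% at 3 days and 2 / 3 / 2% at 30 days. The 30-day widening is smaller than the shortfall because the corrected model also uses each parent's 3-day answer to sharpen the 30-day estimate.
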